5.3. Drug Supplies

Pfizer Global Research and Development will supply dacomitinib (PF-00299804) tablets.

5.3.1. Dosage Form(s) and Packaging

Dacomitinib will be provided as tablets for oral administration. The 45 mg, 30 mg, or 15 mg tablets will be supplied in High Density PolyEthylene (HDPE) bottles for oral administration. The bottles will be properly labeled according to local regulatory requirements.

5.3.2. Preparation and Dispensing

Dispensing will be in bottles provided in quantities appropriate for the study visit schedule. The patient should be instructed to maintain the product in the bottle provided throughout the course of dosing.

Only qualified personnel who are familiar with procedures that minimize undue exposure to them and to the environment should undertake the preparation, handling, and safe disposal of chemotherapeutic agents.

5.4. Administration

Patients will self-administer dacomitinib at their ending dose schedule from the prior study until they experience unacceptable toxicity, tumor progression, or death. Patients will swallow the study medication whole, and will not manipulate or chew the medication prior to swallowing. The tablets will be taken with at least 6 oz. (180 mL) of water on an empty stomach (defined as less than 500 calories within 2 hours before or after intake of study medication).

Patients must be instructed that if they miss a day's dose, they must not make up missed doses on following days, but simply resume the dosing schedule. Likewise, patients must be instructed that if they vomit at any time after taking a dose, they must not "make it up" with an extra dose the same day, but resume subsequent dose the next day as prescribed. Any missed or vomited doses must be indicated in the source documents and Case Report Form (CRF), just as all administered doses are documented.

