This is a multi-center, open-label, treatment extension study open in Japan only. Eligible patients include those with advanced cancer who received and tolerated single-agent dacomitinib in a prior clinical study and have the potential to derive continued clinical benefit based on investigator judgment. Patients enrolled in this extension study may continue to receive dacomitinib starting at the current dose level in the prior study. Dose reductions and re-escalations are allowed based on tolerability. Patients may continue to be treated with dacomitinib on this protocol as long as there is evidence of clinical benefit in the judgment of the investigator. Adverse events will be graded according to NCI CTCAE v4.0, and monitored according to the frequency outlined in the Safety Review Plan.

Study Treatment:

Patients will receive continuous daily dosing of dacomitinib at a dose of 45 mg, 30 mg, or 15 mg. The starting dose of dacomitinib on this treatment extension study will be the patient's ending dose from the prior study.

Patients may continue single-agent dacomitinib treatment on this treatment extension study as long as there is reasonable evidence of clinical benefit without unacceptable toxicity per investigator judgment and with agreement of the Sponsor (see [Section 6.1 Patient Withdrawal](#)).

Statistical Methods:

Due to the nature of this study, the number of patients to be enrolled is not predetermined.

No statistical methods will be employed to test a specific hypothesis in this study. Only descriptive summaries of safety will be provided, and no inferential analyses are planned.

SCHEDULE OF ACTIVITIES

The Schedule of Activities table provides details of the protocol visits and procedures. Refer to the [Study Procedures](#) and [Assessments](#) sections of the protocol for additional information on certain specific procedures and assessments required for compliance with the protocol.

The investigator may schedule visits (unplanned visits), in addition to those listed on the schedule of activities, in order to conduct evaluations or assessments required to protect the well-being of the patient.

Table 1. SCHEDULE OF ACTIVITIES

Protocol Activity	Screening (≤28 days prior to study entry)	Cycle 1 Day 1	Cycles 2 and beyond		End of Treatment	Follow-up Visit ⁹
			Every 8 weeks	Every 6 months		
Informed Consent ¹	X					
Patient History	X					
Registration		X				
Laboratory						
Hematology ²	X		X		X	
Blood Chemistry ³	X		X		X	

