2. STUDY OBJECTIVES AND ENDPOINTS

2.1. Objectives

2.1.1. Primary Objective

- To allow access to dacomitinib for patients who received dacomitinib on a prior study in Japan and who have the potential to derive continued clinical benefit from single-agent dacomitinib treatment without unacceptable toxicity based upon the investigator's judgment.

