3. STUDY DESIGN

This is a multi-center, open-label, treatment extension study open in Japan only. Eligible patients include those with advanced cancer who received and tolerated single-agent dacomitinib in a prior clinical study and have the potential to derive continued clinical benefit based on investigator judgment. Patients enrolled in this extension study may continue to receive dacomitinib starting at the current dose level in the prior study. Dose reductions and re-escalations are allowed based on tolerability. Patients may continue to be treated with dacomitinib on this protocol as long as there is evidence of clinical benefit in the judgment of the investigator. Adverse events will be graded according to NCI CTCAE v4.0, and monitored according to the frequency outlined in the Safety Review Plan.

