5.5. Dose Modification

Dacomitinib will be available at 3 dose strengths, 45 mg, 30 mg, and 15 mg once daily.

Table 2 outlines dose modifications that will apply to patients order to manage treatment-related toxicity that is not controlled by optimal supportive care, or not tolerated due to symptomatology or interference with normal daily activities regardless of severity.

Table 2. Doses of Study Drug Administered

Dose level	Dacomitinib
Level 0	45 mg
Level -1	30 mg
Level -2	15 mg

Dose reductions may take place whenever toxicity that is not controlled with optimal supportive care is noted during the trial. If a patient subsequently tolerates therapy well in the judgment of the investigator, resumption of the next higher dose level may be undertaken. If a patient still cannot tolerate treatment after a dose reduction to the lowest dose of 15 mg, treatment will be discontinued. If a patient is responding to dacomitinib but is requiring a dose modification below 15 mg, the investigator must discuss the situation with the Sponsor's Medical Monitor.

For Grade 3, Grade 4, or intolerable Grade 2 toxicity, treatment will be interrupted. Upon recovery to Grade ≤ 2 or baseline, and per the clinical judgment of the investigator and agreement of the patient, the treatment will be resumed:

- For treatment interruption due to Grade 3 or intolerable Grade 2 toxicity, treatment may be resumed at the same or a lower dose level;
- For episodes of Grade 4 toxicity, reduction to the next lowest dose level is mandated.

If the patient fails to recover within 2 weeks of discontinuation, treatment will be discontinued unless there is discussion of the clinical circumstance with the Sponsor and agreement that the patient may resume treatment after a lapse of greater than 2 weeks. The patient will undergo end of treatment evaluations and follow-up visit as per [Schedule of Activities](#).

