6.1. Patient Withdrawal

Patients may withdraw from the study at any time at their own request, or they may be withdrawn at any time at the discretion of the investigator or Sponsor for safety or behavioral reasons, or the inability of the patient to comply with the protocol-required schedule of study visits or procedures at a given study site. Reasons for withdrawal include, but are not limited to the following:

- Progressive disease;
- Unacceptable toxicity;
- Global deterioration of health-related symptoms;
- Study non-compliance;
- Pregnancy;
- Patient request;
- Lost to Follow-Up;
- Study termination by Sponsor.

If a patient requires more than 2 consecutive weeks of dosing interruption, a discussion should be held with the Sponsor to determine whether or not to withdraw the patient from the study.

If a patient does not return for a scheduled visit, every effort should be made to contact the patient. All attempts to contact the patient and information received during contact attempts must be documented in the patient's medical record. In any circumstance, every effort should be made to document patient outcome, if possible. The investigator should inquire about the reason for withdrawal, request the patient to return all unused investigational product(s), request the patient to return for a final visit, if applicable, and follow up with the patient regarding any unresolved adverse events.

If the patient withdraws from the study, and also withdraws consent for disclosure of future information, no further evaluations should be performed, and no additional data should be collected. The Sponsor may retain and continue to use any data collected before such withdrawal of consent.

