7.1. Pregnancy Testing

For female patient of childbearing potential, a serum or urine pregnancy test, with sensitivity of at least 25 mIU/mL, will be performed at screening, before investigational product administration at the baseline visit, and at the end of treatment visit. A negative pregnancy result is required before the patient may receive the investigational product. Pregnancy tests will also be done whenever 1 menstrual cycle is missed during the active treatment period (or when potential pregnancy is otherwise suspected), and at the end of the study to confirm the patient has not become pregnant during the study. Pregnancy tests may also be repeated as per request of institutional review boards (IRBs)/ethics committees (ECs) or if required by local regulations.

In the case of a positive confirmed pregnancy, the patient will be withdrawn from study medication and from the study.

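### Section 5.4 ends dosing at tumor progression without exception, Section 3 and the synopsis continue on judged benefit, and Section 6.1 does not settle which applies or who decides

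*Protocol*

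**What the plan says.** The protocol addresses how long treatment lasts in four places.

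- **Section 5.4 (Administration)**: patients take the drug "until they experience unacceptable toxicity, tumor progression, or death". No exception is given and no decision-maker is named.
- **Section 3 (Study Design)**: treatment may go on "as long as there is evidence of clinical benefit in the judgment of the investigator". Progression is not mentioned.
- **Synopsis, Study Design**: the same text as Section 3.
- **Synopsis, Study Treatment**: treatment may go on "as long as there is reasonable evidence of clinical benefit without unacceptable toxicity per investigator judgment and with agreement of the Sponsor", with a reference to Section 6.1.

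Section 6.1 introduces its list with "Reasons for withdrawal include, but are not limited to the following"; progressive disease is one entry. On prolonged dosing interruption (more than 2 consecutive weeks) it says that "a discussion should be held with the Sponsor to determine whether or not to withdraw the patient from the study". It has no step for Sponsor agreement to continue on the ground of benefit.

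The primary objective (Section 2.1.1) begins "To allow access to dacomitinib for patients who received dacomitinib on a prior study in Japan", so access to the drug is the purpose of the study.

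**The concern.** Take a patient whose tumor has progressed but who, in the investigator's view, still benefits. Section 5.4 ends dosing. Section 3 lets the investigator continue it. The Study Treatment part of the synopsis lets it continue only if the Sponsor also agrees. Sites that follow different passages would treat the same patient for different lengths of time.

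What depends on this is the length of access, the exposure and discontinuation reasons summarized under Section 9.3, and the adverse event window in Section 8.2. The Sponsor-agreement condition would limit differences between sites if it were applied, but it stands only in the synopsis. Tumor results need not be entered on the CRF (Section 7.5), so dosing past progression may not be identifiable from the CRF alone.

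**Working it through.** The protocol states no sample size, hypothesis test or planned duration, so there is no figure to reproduce. The check is a comparison of the passages.

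**1. The rules side by side**

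| Place | What governs treatment | Who decides | Progression named? |
|---|---|---|---|
| Section 5.4 | Ends at a listed event | Not stated | Yes, as an end event |
| Section 3 | Continues on judged benefit | Investigator | No |
| Synopsis, Study Design | Continues on judged benefit | Investigator | No |
| Synopsis, Study Treatment | Continues on judged benefit without unacceptable toxicity | Investigator with Sponsor agreement | No |

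Statements: 1 + 1 + 1 + 1 = 4. Section 3 and the synopsis Study Design text coincide, which leaves 3 distinct rules. The synopsis also differs within itself on whether the Sponsor must agree.

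**2. Does Section 6.1 settle it?** It does not. Progression is in the list, but nothing there says whether withdrawal must follow. Pregnancy is in the same list, and Section 7.1 makes it binding in a separate sentence: "the patient will be withdrawn from study medication and from the study". Apart from Section 5.4, no sentence does that for progression. Section 6.1 is therefore compatible with Section 5.4, but it neither confirms that rule nor grants discretion to continue. The discretion it gives to the investigator or Sponsor concerns safety, behavior and inability to keep to visits or procedures.

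**3. Does the protocol write exceptions where it wants them?** Section 5.5 does so for failure to recover within 2 weeks: "treatment will be discontinued unless there is discussion of the clinical circumstance with the Sponsor and agreement that the patient may resume treatment". Section 5.4 has no comparable clause. Section 5.10 lets the investigator, in consultation with the Sponsor, agree that starting a bisphosphonate is not progression. That governs what counts as progression, not what follows from it. Without such agreement the patient is deemed to have progressed, so the conflict can arise even without an imaging finding.

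**4. Effect on the observation windows.** Let progression fall on day P and let dosing run d further days. Section 8.2 ends SAE reporting 28 days after the last dose; the Schedule of Activities puts the follow-up visit 28 to 35 days after treatment stops.

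| | Stop at progression | Continue d days | Difference |
|---|---|---|---|
| Last dose | P | P + d | d |
| End of SAE period | P + 28 | P + d + 28 | d |
| Follow-up visit | P + 28 to P + 35 | P + d + 28 to P + d + 35 | d |

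The document gives neither d nor the number of patients concerned, so the total cannot be computed.

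**5. Minor point on entry.** Section 5.5 interrupts treatment for 3 toxicity categories (Grade 3, Grade 4, intolerable Grade 2). Inclusion criterion 2 names 2 of them as ongoing related events that bar entry; Grade 4 is absent.

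**The case against.** The strongest reply is that the passages can be read together. Section 3 and the synopsis say that patients *may* continue while benefit lasts, which can be taken as a necessary condition operating beneath the end events in Section 5.4. No passage expressly permits dosing after progression. This reading is possible, but no passage ranks the rules and none equates progression with loss of benefit, so a site has no textual ground for preferring it.

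Second, Section 6.1 says patients may be withdrawn at the discretion of the investigator or Sponsor, so it does name decision-makers. That clause is tied to safety, behavior and non-compliance, and it does not say who decides on continuation after progression.

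Third, the inference from the exception in Section 5.5 does not prove what was intended in Section 5.4. That is fair; it shows only that the protocol had a form of words available and did not use it there.

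Fourth, the reporting windows are designed to move with the last dose, so the day arithmetic describes a consequence and not a separate fault. That also stands.

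Fifth, the practical harm is limited. Doses are documented (Section 5.4), tumor results are in the clinic chart (Section 7.5), monitors have access to source records (Section 10), and efficacy is not analyzed (Section 9.2). This limits the weight of the point without removing the conflict.

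On Grade 4, several safeguards make the practical effect small: Section 3 requires that prior treatment was tolerated, exclusion criterion 4 covers conditions that raise risk, the Sponsor approves each enrollment (Section 4.3), and Section 5.5 interrupts dosing. Exclusion criterion 1, on withdrawal criteria met in the prior study, may help too, but the prior protocols are not at hand.

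**Conclusion.** The concern holds. The protocol gives three rules for when treatment ends, and for a patient with progression but judged benefit they lead to different treatment durations. The section to which the synopsis refers does not decide between them or say whose decision prevails. This is an inconsistency in the current text, not a detail left for later.

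Its size in patients or days is unknown. It bears on the primary objective (access) and on the descriptive summaries of exposure and discontinuation reasons; no error rate, power or inference is affected. Dosing past progression could be recovered from source records. The conclusion assumes that at least one patient progresses while judged to benefit, and that no text outside the protocol ranks the passages. It should be corrected. The Grade 4 omission is minor.

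**What to change.** Reconcile Section 5.4, Section 3, both synopsis statements and Section 6.1 so that one rule, chosen by the sponsor, says whether progression alone ends treatment and who decides. If Sponsor agreement is part of that rule, state it in the body as well as in the synopsis, and make the reference to Section 6.1 lead to text that contains it. Which clinical rule applies is for the sponsor.

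As a minor item, reconcile inclusion criterion 2 with Section 5.5, so that the absence of Grade 4 is either corrected or shown to be intended.

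The cost is wording in the synopsis, Sections 3, 5.4 and 6.1, and one phrase in Section 4.1. No patients, visits or procedures are added.

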5.5. Dose Modification

Dacomitinib will be available at 3 dose strengths, 45 mg, 30 mg, and 15 mg once daily.

Table 2 outlines dose modifications that will apply to patients order to manage treatment-related toxicity that is not controlled by optimal supportive care, or not tolerated due to symptomatology or interference with normal daily activities regardless of severity.

Table 2. Doses of Study Drug Administered

Dose level	Dacomitinib
Level 0	45 mg
Level -1	30 mg
Level -2	15 mg

Dose reductions may take place whenever toxicity that is not controlled with optimal supportive care is noted during the trial. If a patient subsequently tolerates therapy well in the judgment of the investigator, resumption of the next higher dose level may be undertaken. If a patient still cannot tolerate treatment after a dose reduction to the lowest dose of 15 mg, treatment will be discontinued. If a patient is responding to dacomitinib but is requiring a dose modification below 15 mg, the investigator must discuss the situation with the Sponsor's Medical Monitor.

For Grade 3, Grade 4, or intolerable Grade 2 toxicity, treatment will be interrupted. Upon recovery to Grade ≤ 2 or baseline, and per the clinical judgment of the investigator and agreement of the patient, the treatment will be resumed:

- For treatment interruption due to Grade 3 or intolerable Grade 2 toxicity, treatment may be resumed at the same or a lower dose level;
- For episodes of Grade 4 toxicity, reduction to the next lowest dose level is mandated.

If the patient fails to recover within 2 weeks of discontinuation, treatment will be discontinued unless there is discussion of the clinical circumstance with the Sponsor and agreement that the patient may resume treatment after a lapse of greater than 2 weeks. The patient will undergo end of treatment evaluations and follow-up visit as per [Schedule of Activities](#).

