4.1. Inclusion Criteria

Patient eligibility should be reviewed and documented by an appropriate member of the investigator's study team before patients are included in the study.

Patients must meet all of the following inclusion criteria to be eligible for enrollment into the study:

1. Received dacomitinib on another clinical trial in Japan and judged by the investigator to be deriving ongoing clinical benefit.
2. No ongoing NCI CTCAE Grade 3 or intolerable Grade 2 adverse events related to dacomitinib treatment on the prior study.
3. Evidence of a personally signed and dated informed consent document indicating that the patient (or a legally acceptable representative) has been informed of all pertinent aspects of the study.
4. Patients who are willing and able to comply with scheduled visits, treatment plan, laboratory tests, and other study procedures.
5. Male and female patients of childbearing potential and at risk for pregnancy must agree to continue to use a highly effective method of contraception throughout the study and for at least 90 days after the last dose of assigned treatment.

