5.6. Adverse Event Management

Specific guidance which has been developed for the management of common EGFR tyrosine kinase inhibitor toxicity at various grades is provided in [Appendix 1](#). In general (and not as substitute for consideration of the more specific guidance in [Appendix 1](#)):

For diarrhea, patients should begin therapy with loperamide at first evidence of increased frequency of bowel movement with adjustment in dose or prescription of alternative medication when necessary. The potential need for increased oral hydration (including electrolyte-containing fluids) should also be evaluated. There is a risk of pre-renal azotemia noted from poor fluid intake in the face of diarrhea and/or stomatitis. Monitor renal function tests and consider supplemental IV hydration if necessary.

For prevention of dry skin, patients should begin a regimen of moisturizers prior (ideal) or with start of dosing, and use appropriate measures to prevent excessive sun exposure.

Treatment of acneiform rash may include topical steroids, topical antibiotics, and oral antibiotics.

Mucositis can be treated with antibiotic-free oral rinse; chlorhexidine should be avoided.

Other measures may be utilized per the investigator judgment or emerging data-driven guidelines where these are available

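### Section 5.5 lets dacomitinib restart one grade earlier than Appendix 1 after Grade 3–4 diarrhea and Grade 3 keratoconjunctivitis, and at an unreduced dose after the latter; no text says which rule governs

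*Protocol*

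**What the plan says.** Section 5.5 gives the interruption rule: "For Grade 3, Grade 4, or intolerable Grade 2 toxicity, treatment will be interrupted". The restart condition follows: "Upon recovery to Grade ≤ 2 or baseline, and per the clinical judgment of the investigator and agreement of the patient". After Grade 3 or intolerable Grade 2 toxicity, "treatment may be resumed at the same or a lower dose level"; after Grade 4, a step down is mandatory. A time limit depends on the same notion of recovery: "If the patient fails to recover within 2 weeks of discontinuation, treatment will be discontinued", unless the case is discussed with the Sponsor and resumption is agreed.

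Section 5.6 introduces Appendix 1: "Specific guidance which has been developed for the management of common EGFR tyrosine kinase inhibitor toxicity at various grades is provided in" that appendix. It adds that its own general advice does not replace considering the appendix.

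Appendix 1 gives study-treatment instructions for two toxicities:

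- **Diarrhea.** Grade 3 and Grade 4 are held until Grade 1 or lower. A one-level reduction is to be considered after Grade 3 and is mandatory after Grade 4. Grade 2 that has not improved within 24 hours on loperamide is held until Grade 1.
- **Keratoconjunctivitis.** Grade 3 is held until Grade 1 or lower, then reduced one level. Grade 2 lasting 2 weeks or more is handled the same way.

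For acneiform rash, dry skin, paronychia, pruritus and mucositis, Appendix 1 sets no restart grade.

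**The concern.** Both texts tell the investigator when to restart the drug after the same events, and they give different answers. Section 5.5 does not cite Appendix 1, and Appendix 1 does not cite 5.5. Two sites could handle identical patients differently and each point to the protocol.

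What is at stake is re-treatment before a serious toxicity has settled as far as the protocol's own toxicity guidance asks, or at a dose which that guidance says to lower. Section 5.6 itself warns of kidney effects when fluid intake is poor during diarrhea. The 2-week limit is drawn in as well, because whether a patient has recovered in time depends on which restart grade is used.

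**Working it through.** There is no plan figure to reproduce: the study has no predetermined sample size and no hypothesis test. The check sets the two texts side by side.

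**Inputs.** Triggers, restart grade and restart dose come from Section 5.5. Restart grades and doses by toxicity come from the Appendix 1 tables.

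**Formula.** Fall in grade needed = grade at interruption − highest grade at which restart is allowed.

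| Event | Fall needed, 5.5 | Fall needed, Appendix 1 | Restart dose, 5.5 | Restart dose, Appendix 1 |
|---|---|---|---|---|
| Diarrhea, Grade 3 | 3 − 2 = 1 | 3 − 1 = 2 | same or lower | consider one level lower |
| Diarrhea, Grade 4 | 4 − 2 = 2 | 4 − 1 = 3 | lower, mandatory | lower, mandatory |
| Keratoconjunctivitis, Grade 3 | 3 − 2 = 1 | 3 − 1 = 2 | same or lower | one level lower |
| Diarrhea, intolerable Grade 2, not improved within 24 hours on loperamide | 2 − 2 = 0 | 2 − 1 = 1 | same or lower | reduction considered only on recurrence |
| Keratoconjunctivitis, intolerable Grade 2, lasting 2 weeks or more | 2 − 2 = 0 | 2 − 1 = 1 | same or lower | one level lower |

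**Grade.** The gap is 1 grade in every row. The first 3 rows differ without further condition. The last 2 differ only when the event is intolerable, because 5.5 does not interrupt for tolerable Grade 2. That makes 3 + 2 = 5 rows, in 2 of the 7 toxicities Appendix 1 covers.

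**Dose.** The texts differ for Grade 3 keratoconjunctivitis and, conditionally, for Grade 2. They are compatible for diarrhea.

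**Two-week rule.** Take Grade 3 diarrhea that settles at tolerable Grade 2. Under 5.5 the patient has met the grade condition, and treatment may resume if investigator and patient agree. Under Appendix 1 the hold continues, and once it passes 2 weeks the case goes to discontinuation or Sponsor discussion.

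**Precedence.** The only sentence bearing on the standing of Appendix 1 is the parenthesis in 5.6. It introduces that section's own supportive-care list, asks that the appendix be considered, and does not mention the restart rule. Where the protocol means one text to override another it says so: in Section 5.7, labeling supersedes the reference safety document on storage conditions.

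**The case against.** The strongest reply is that this is a general rule beside specific guidance. Section 5.6 follows directly and sends sites to Appendix 1, and reading the specific over the general is natural. The 5.5 dose wording is permissive, so a reduction after keratoconjunctivitis complies with it. A site that follows the stricter text satisfies both. All of this is fair and limits the weight of the point. It does not remove it, because no site is told to follow the stricter text and 5.5 as written permits the other course.

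Three stronger readings are tempting, and the documents do not support them.

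- A reader might infer that an intolerable Grade 2 event can restart at once, since it already satisfies the grade condition. But 5.5 also requires recovery, investigator judgment and patient agreement, and an event that is still intolerable would meet the interruption trigger again. The missing word is a drafting matter, not a separate defect.
- A reader might infer that restarting under 5.5 breaches a prohibition. Appendix 1 is titled as guidelines and 5.6 calls it guidance, so a departure on documented judgment is not clearly forbidden.
- A reader might infer overdosing from Table 2, where the unreduced dose is 45/30 = 1.5 or 30/15 = 2.0 times the next level down. The comparison is with the patient's own assigned dose, not with exposure above it, and 5.5 allows return to the next higher level once therapy is well tolerated.

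**Conclusion.** The concern holds as an unresolved conflict between two stated re-dosing rules: one grade in three situations, one grade in two more when the event is intolerable, and one dose level after keratoconjunctivitis. It is a minor to moderate patient-safety point that should be fixed. Investigator judgment, patient agreement, the pointer in 5.6 and the Sponsor discussion of holds beyond 2 weeks (5.5 and 6.1) all reduce the risk. The descriptive safety analysis is not affected.

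The conclusion rests on the wording alone. The documents give no frequency for these events in this population, so the number of patients affected cannot be estimated.

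**What to change.** Amend Section 5.5 as follows.

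- State that where Appendix 1 gives a study-treatment hold, resume or dose instruction, it applies in place of the general rule. This should not delay the immediate 5.5 interruption for intolerable Grade 2 toxicity.
- Keep return to the patient's baseline grade at entry as recovery. The entry criterion, "No ongoing NCI CTCAE Grade 3 or intolerable Grade 2 adverse events related to dacomitinib treatment on the prior study", admits patients with tolerable Grade 2 events. Without this exception such a patient could stay on hold after returning to baseline.
- Use the same definition of recovery for the 2-week rule, and keep the Sponsor waiver.
- As a clarification, change the general threshold to *tolerable Grade ≤ 2 or baseline*.
- For a patient at 15 mg who would need a further reduction, leave the existing rules as they are. Treatment stops if 15 mg is not tolerated. The Medical Monitor route is only for responders: "If a patient is responding to dacomitinib but is requiring a dose modification below 15 mg, the investigator must discuss the situation". It should not be extended to every patient at 15 mg.
- Set no Grade 1 threshold for the five toxicities where Appendix 1 has none. The primary objective is continued access ("To allow access to dacomitinib for patients who received dacomitinib on a prior study in Japan"), and a blanket tightening would work against it.

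The cost is a wording amendment, with no added visits or patients. Holds for diarrhea and keratoconjunctivitis become slightly longer, and some more cases reach Sponsor discussion.
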